To assess rebound insomnia, both categorical analysis at the subject level and continuous analysis at the group mean level will be performed. For each of the first 3 nights and each of the 2 weeks of the Follow-up Period the proportion of subjects whose corresponding value for sSOL or sWASO exceeds the corresponding Screening Period value by 5 minutes will be summarized by treatment group and compared to placebo. The percentage of ‘rebounders’ between each treatment and placebo group will be analyzed using a Cochran-Mantel-Haenszel test, adjusted for country and age group.

To assess statistical significance using the continuous data at the group mean level, the data will be analyzed using ANCOVA, adjusted for country, age group and treatment. The LS mean of each of the first 3 nights and each week of the Follow-up Period will be compared to the Screening Period between each treatment group and placebo. If the lower bound of the 95% CI of sSOL or sWASO for each of the first 3 nights and the mean of each week of the Follow-Up Period exceeds the upper bound of a 95% CI for the values during the Screening Period in the given treatment group, it will be considered strong evidence for rebound insomnia. If the LS means for sSOL and sWASO for the Follow-up Period are all lower than for the Screening Period, then no rebound insomnia is suggested. Otherwise, the degree to which the parameters worsen, and the time point(s) at which they worsen will be considered to evaluate whether clinically meaningful rebound insomnia is present.

To evaluate morning sleepiness item on the Sleep Diary, the mean change from Study Baseline of the 1st 7 mornings after the 1st dose in Period 1, Month 1, Month 3 and Month 6 will be analyzed using MMRM, assuming MAR. Additionally, morning sleepiness change from both Study Baseline and Period 2 Baseline for the 1st 7 mornings after the 1st dose in Period 2, Month 9, and Month 12, and also the change from Screening of each of the 2 weeks of the Follow-Up Period will be summarized with mean and 95% CI's. (revised per Amendment 03)

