 - The sleep onset responder is defined as: sSOL at Study Baseline (or Period 2 Baseline) is >30 minutes and mean sSOL at each month (Months 7, 8, 9, 10, 11 and 12) is ≤ 20 minutes,
 - The sleep maintenance responder is defined as: sWASO at Study Baseline (or Period 2 Baseline) is >60 minutes and mean sWASO at each month (Months 7, 8, 9, 10, 11

and 12) is ≤ 60 minutes and shows a reduction of >10 minutes compared to Study Baseline (or Period 2 Baseline).

The proportion of responders will be analyzed based on the subjects with sSOL > 30 minutes at the baseline for sSOL and separately the subjects with sWASO > 60 minutes at the baseline for sWASO.

- Morning sleepiness item of the Sleep Diary:
 - Change from Study Baseline of mean rating on morning sleepiness at the 1st 7 mornings after the 1st dose in Treatment Period 1, Month 1, Month 2, Month 3, Month 4, Month 5 and Month 6.
 - Change of mean rating on morning sleepiness from Study Baseline / Treatment Period 2 Baseline for 1st 7 mornings after the 1st LEM dose, 1, 3, 6, 9 and 12 months of exposure to LEM5 and LEM10. Data from subjects randomized to LEM5 or LEM10 at the start of the study will use Study Baseline, data from subjects who were re-randomized to LEM5 or LEM10 in Period 2 will use Treatment Period 2 Baseline. Change from Screening of mean rating on morning sleepiness of 1st 7 mornings and 2nd 7 mornings in Follow-Up Period.
- Rebound insomnia endpoints during the Follow-up Period as follows:
 - Change from Screening of sSOL on each of the 1st 3 nights, mean sSOL of the 1st 3 nights, mean sSOL of the 1st 7 nights, and mean sSOL of the 2nd 7 nights of the Follow-up Period
 - Change from Screening of sWASO on each of the 1st 3 nights, mean sWASO of the 1st 3 nights, mean sWASO of the 1st 7 nights and mean sWASO of the 2nd 7 nights of the Follow-up Period
 - Proportion of subjects whose sSOL is longer than at Screening by at least 5 minutes for each of the 1st 3 nights, mean sSOL of the 1st 3 nights, mean of the 1st 7 nights, and mean of the 2nd 7 nights of the Follow-up Period
 - Proportion of subjects whose sWASO is higher than at Screening by at least 5 minutes for each of the 1st 3 nights, mean sWASO of the 1st 3 nights, mean of the 1st 7 nights, and mean of the 2nd 7 nights of the Follow-up Period.

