The actual value of sSOL and sWASO will be analyzed separately using analysis of covariance model (ANCOVA) with factors of age group (<65 , and ≥ 65 years older), region (North America, Europe and New Zealand, Asia), and treatment for each time point (baseline, each of the first 3 nights, mean of the first 3 nights, mean of the first 7 nights, and mean of the last 7 nights of the Follow-up Period). The 95% CI of the treatment difference will be constructed for each time point. It will be considered as strong evidence of rebound insomnia if the lower bound of the 95% CI of sSOL or sWASO for each of the 3 nights, the mean of the first 3 nights, mean of the first 7 nights, and mean of the second 7 nights of the Follow-up Period exceeds the upper bound of a 95% CI for the values during the Screening Period in the given treatment group. If the LS means for sSOL and sWASO for the Follow-up Period are all lower than for the Screening Period, then no rebound insomnia is suggested. In this analysis, the treatment groups will be defined as the last randomized study treatment just before the Follow-up period.

- Analyses for persistence versus loss of effect will be conducted for sSOL, sSE, sWASO and sTST at Months 2 through Month 12 compared to Month 1.

The 95% CI for the change from Study Baseline of sSOL, sSE, sWASO and sTST at each visit will be calculated using the MMRM model assuming MAR (no missing value imputation) with factors of age group (<65, and ≥65 years older), region (North America, Europe and New Zealand, Asia), treatment, visit and treatment-by-visit interaction as fixed effect, and baseline value as covariate based on FAS. At each month beyond Month 1, the change from Study Baseline will be compared to either the lower bound of the 95% CI (for sSE and sTST) or the upper bound of the 95% CI (for sSOL and sWASO) at Month 1. Persistence of effect will be defined as present if the mean change from Study Baseline at Month 6 is above the lower bound of the 95% CI at Month 1 for sSE or sTST and below the upper bound of the 95% CI at Month 1 for sSOL and sWASO.

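### The SAP's only group-level criterion for strong evidence of rebound insomnia is non-overlap of two unpaired 95% CIs; this is far stricter than a paired 95% comparison and, if read jointly, cannot recognise a rebound confined to nights 1 to 3.

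*SAP*

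**What the plan says.** SAP 3.4.2.4 lists the rebound endpoints as within-subject changes, for example "Change from Screening of sSOL on each of the 1st 3 nights", and as proportions of subjects at least 5 minutes worse than at Screening. Both are given for nights 1, 2 and 3, the 3-night mean, and each of the two Follow-up weeks.

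The model paragraph does something different: "The actual value of sSOL and sWASO will be analyzed separately using analysis of covariance model (ANCOVA) with factors of age group". Besides age, the model holds only region and randomized treatment, and it is fitted afresh at every time point. Screening is neither a covariate nor a listed time point. The listed reference is baseline, which SAP 6.1.1 defines for diary data from the last 7 mornings of the Run-In Period.

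The decision rule works within a treatment group. Strong evidence is declared when the lower Follow-up limit, for either measure, "exceeds the upper bound of a 95% CI for the values during the Screening Period in the given treatment group". The Follow-up side of the comparison names six time points: three single nights, their average, and the two weekly averages. The list closes with "and mean of the second 7 nights of the Follow-up Period", so its items are joined by a plain conjunction. When every Follow-up LS mean lies below Screening, the SAP takes this to suggest no rebound. It says nothing about results in between.

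Protocol 9.7.1.6.2 uses the same non-overlap rule ("it will be considered strong evidence for rebound insomnia") and the same statement about no rebound. It then adds a third provision: otherwise, the size and timing of any worsening are weighed to decide whether there is clinically meaningful rebound.

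**The concern.** The question is whether a subject sleeps worse after stopping than that same subject did at Screening. The data are paired, and the endpoint is defined as a paired change. Comparing the ends of two separately fitted intervals discards the pairing and adds the two margins of error in full. It therefore needs a much larger worsening than a 95% CI on the change would need.

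The list of time points adds a second problem. Read as a joint condition, the second-week mean must also clear Screening, so a rebound that settles within days cannot qualify. Naming nights 1, 2 and 3 separately shows that early rebound is of interest.

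Rebound after discontinuation is a stated secondary objective (protocol 8.2, SAP 1.1.2), and protocol 9.5.3 counts it among the safety-related assessments.

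**Working it through.** The documents give no power or error rate for this rule, so there is no stated figure to reproduce.

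**Inputs from the documents**
- 300 randomized per arm; 120 per arm left at Month 12 in the plan's worst case (protocol 9.7.2, SAP 2).
- Placebo subjects are re-randomized about 1:1 to the two doses (protocol 9.4.3). Follow-up groups are defined by last randomized treatment (SAP 3.4.2.4).
- Subjects per dose at Follow-up: worst case 120 + 120/2 = 180; full retention 300 + 300/2 = 450.
- SD 33 min, the planning SD for change in sSOL.

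**Assumptions**
- The SD of a weekly mean value is about 33 min (the SD of change used as a proxy).
- The correlation rho between Screening and Follow-up is 0.3, 0.5 or 0.7.
- Within-night SD is 25 min. Data are normal, the same subjects are present at both times, and age and region are left out.

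**Error at one time point, equal standard errors**
The intervals separate when the difference exceeds 2 x 1.96 x SE. The SE of the paired difference is SE x sqrt(2(1 - rho)). So non-overlap requires z > 3.92 / sqrt(2(1 - rho)).
- rho 0.3: z = 3.31, one-sided error 0.00046
- rho 0.5: z = 3.92, one-sided error 0.000044
- rho 0.7: z = 5.06, one-sided error 0.0000002
- Paired 95% CI: z = 1.96, one-sided error 0.025

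**Worsening needed, weekly mean, n = 180**
SE = 33/sqrt(180) = 2.46 min.
- Non-overlap: 3.92 x 2.46 = 9.6 min.
- Paired, 1.96 x 2.46 x sqrt(2(1 - rho)): 5.7, 4.8 and 3.7 min for rho 0.3, 0.5 and 0.7.
- For a true 10-min worsening, non-overlap is met with probability of about 55-58% and the paired criterion with 93-99.9%.

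**Joint reading, rebound on nights 1-3 only**
Week 2 is back at the Screening level, yet its interval must also clear. The joint probability therefore cannot exceed the week-2 probability, which is the single-time-point error above (at most about 0.0005). In simulation (1,500 trials per scenario; rebound of 10, 20 or 30 min) the rule was met in 0-0.13% of trials at n = 180 and 0% at n = 450. A larger early rebound does not help.

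**Per-time-point reading, 10 min on nights 1-3, judged on the 3-night mean**
- Non-overlap: 50-52% at n = 180; 97-99.8% at n = 450.
- Paired CI: 92-99.9% at n = 180; above 99.9% at n = 450.

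**Joint reading, rebound lasting all 14 nights**
- 10 min: 15-22% at n = 180; 86-94% at n = 450.
- 20 min: 99-100%.

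**The case against.** The strongest reply is that this rule sets the bar for strong evidence and is not the whole assessment. That stands. Change from Screening and the 5-minute proportions are both planned by time point and both use the subject's own Screening value. The protocol's third provision covers a short-lived worsening, and nothing in the SAP withdraws it. A conservative bar for the word strong is also a legitimate choice.

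A reader might infer that a real short-lived rebound would go unnoticed, or that the rule can hardly fire. The documents do not support either. The near-zero figure depends on the joint reading, and the wording also allows a per-time-point reading. A sustained 20-min rebound meets even the joint rule almost always.

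A reader might also infer that the plan leans towards declaring no rebound. However, that statement requires every Follow-up LS mean to be below Screening. If the same subjects supply both means, a clear rise on nights 1 to 3 blocks it and the result is intermediate. Masking by dropout would need poor sleepers to leave selectively, and the documents give no figure for that.

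The other outputs fill the gap only in part:
- The default model in SAP 3.4.2.4 is for change from baseline, and the rebound paragraph replaces it with a model of actual values. Change from Screening is left with descriptive statistics, which SAP 3 lists without a CI.
- Protocol 9.7.1.6.2 compares the 5-minute proportions with placebo, but SAP 3 states that Period 2 has no placebo group, and Follow-up comes after Period 2.
- The SAP does not carry over the intermediate provision, which is where a brief rebound would fall.

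**Conclusion.** The point holds as a weakness in the SAP's only explicit group-level criterion, not as a failure of the whole rebound assessment. Ignoring the pairing cuts the one-sided error at a time point from 0.025 to between about 0.0005 and 0.0000002. The practical loss depends on the reading. Under the joint reading, a rebound limited to nights 1 to 3 is almost never called strong evidence. Under the per-time-point reading, the loss is substantial at the plan's worst-case retention (about 50% against 92% or more for a 10-min effect) and small at full retention.

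The percentages rest on the assumed SD, correlations and night-to-night variation. The ordering of the two methods does not depend on the particular SD, provided Screening and Follow-up values are positively correlated. The mismatch between baseline and Screening in the model list, and the missing intermediate tier, are matters of text and need no assumption. The change is worth making because it is cheap and the objective concerns safety.

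**What to change.** In SAP 3.4.2.4, with matching wording in protocol 9.7.1.6.2:
- Analyse change from the subject's own Screening mean, in subjects with Follow-up data, by ANCOVA with Screening value, age group, region and last treatment.
- Report the LS mean change and 95% CI at each time point separately, and base the group-level rebound assessment on these.
- State that the criterion applies per time point.
- Replace baseline with Screening in the list of model time points.
- Restore the protocol's intermediate tier in the SAP.
- Keep the 5-minute proportions.

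This changes wording and programming only; the data are already collected. The cost is more chance findings. At about 2.5% per comparison, 6 time points x 2 measures x 2 doses = 24 comparisons give an expected 24 x 0.025 = 0.6 flags with no rebound at all. The overall pattern, not a single flag, should therefore be interpreted.

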9.1.2.2 Treatment Period 2 (Period 2)

At the end of Month 6 (Period 2 Baseline), subjects who received PBO during Period 1 will undergo a 2nd randomization to receive either LEM5 or LEM10 (approximately 1:1) during Period 2. Subjects who received lemborexant during Period 1 will continue to receive lemborexant at the same dose level during Period 2. Subjects will not be informed of the timing of the 2nd randomization (at the end of Month 6); allocation of dose will be double blind.

Subjects will continue to complete the Sleep Diary every morning. Sleep diaries will be checked on a monthly basis. The subjects will return to the clinic for the 9- and 12-month visits. In between these clinic visits, at the end of Months 7, 8, 10, and 11, study site personnel will conduct a phone call to the subject to review any issues with completion of the Sleep Diary and to query concomitant medications and AEs.

At each clinic visit, safety and tolerability will be assessed, the eC-SSRS will be completed, a urine drug test will be conducted, the Sleep Diary will be reviewed for completeness, compliance will be checked, and drug will be dispensed (except at the end of Month 12). At the end of Months 9 and 12, the ISI, FSS, the EQ-5D-3L, the PGI-Insomnia and the WPAI-GH will be completed. At predefined visits, a blood sample will be collected for PK analysis.

Period 2 will end with the completion of the 12-month visit. For analysis purposes, a subject who completes assessments through Period 2 will be defined as a study completer.

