9.1.2.3 Follow-Up Period

The Follow-up Period will begin at the end of Period 2. Subjects will cease to take study drug but will continue to complete the Sleep Diary each morning until the End of Study visit.

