Day	-35 to -17	-17 to -14 ^f	thru -1	1																	
Month ^g	-	-				1	2	3	4	5	6	7	8	9	10	11	12	(Wk 52 to 54)	(End Wk 54)		
Procedures/ Assessments																					
PGI-Insomnia						X		X			X			X			X				
T-BWSQ																			X		
Adverse events ¹	←----->																				
Lemborexant PK sampling (plasma) ^u						X		X			X			X			X			X ^v	X

Footnotes for Table 3 (revised per Amendments 01 and 03)

AE = adverse event; β -hCG = beta-human chorionic gonadotropin; ECG = electrocardiogram; eC-SSRS = electronic Columbia-Suicide Severity Rating Scale; EDD = Early Drug Discontinuation; EOS = End of Study; EQ-5D-3L = EuroQOL version 5D-3L; ET = early termination; PGI-Insomnia = Patient Global Impression - Insomnia; PK = pharmacokinetics; T-BWSQ = Tyrer Benzodiazepine Withdrawal Symptom Questionnaire; UNS = unscheduled, WPAI-GH = Work Productivity and Activity Impairment Questionnaire – General Health.

- a: Subjects will not be informed that placebo will be administered during the Run-In Period. They will also not be informed of the timing of the placebo-controlled period (Period 1) or the active-treatment (only) period (Period 2), and will not be informed of the timing of the 2nd randomization for subjects who received placebo during Period 1.
- b: These assessments will be conducted at EOS, ET and EDD (except the T-BWSQ, which will not be conducted at EDD). Subjects who discontinue study drug prematurely at any time after randomization at Visit 3 (Study Baseline) will be encouraged to return to the site as soon as practicable (preferably within 7 days). These subjects will be encouraged to continue to complete all study assessments (excepting PK samples, which will not be taken), including the Sleep Diary, and to return for all subsequent clinic visits, without the administration of study medication. Subjects who do not agree to this will undergo an ET Visit and an EOS Visit. Subjects who do agree to continue with study procedures without the administration of study drug will undergo an EDD Visit. (revised per Amendment 01) These subjects need not attend the next regularly scheduled visit if this falls within the visit window of the next visit. Subjects who discontinue early from study drug are considered on study as long as they return for their regularly scheduled visits.
- c: Assessments during an UNS to be performed at the discretion of the investigator.

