9.5.5 Completion/Discontinuation of Subjects

For purposes of entering subject disposition in the eCRF, a subject will be considered to have completed the study per protocol after the End of Study visit has been completed. The subject may elect to discontinue the study at any time for any reason. Subjects who discontinue study drug prematurely at any time after randomization at Visit 3 (Study Baseline) will be encouraged to return to the site as soon as practicable (preferably within 7 days). These subjects will be encouraged to continue to complete all study assessments (excepting PK samples, which will not be taken), including the Sleep Diary, and to return for all subsequent clinic visits, without the administration of study medication.

Subjects who agree will undergo an EDD Visit, during which all assessments will be conducted that would be made at an ET visit (except the T-BWSQ). These subjects need not attend the next regularly scheduled visit if this falls within the visit window of the next visit. Subjects who discontinue early from study drug are considered on study as long as they return for their regularly scheduled visits.

Subjects who do not agree to this will undergo an ET Visit and an EOS Visit, as described in the Schedule of Procedures/Assessments (Table 3). (revised per Amendment 01)

Subjects who withdraw because of an AE should also undergo a urine drug test.

If the investigator or sponsor discontinues a subject from the study prematurely, the investigator will promptly explain to the subject involved that the study will be discontinued for that subject and will provide appropriate referral for medical treatment and other necessary measures for the subject. A subject who has ceased to return for visits will be followed up by mail, phone, or other means to gather information such as the reason for failure to return, the status of treatment compliance, the presence or absence of AEs, and clinical courses of signs and symptoms. This information will be recorded in the CRF.

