3.6.7.2 Tyrer Benzodiazepine Withdrawal Symptom Questionnaire (T-BWSQ)

Withdrawal symptoms are assessed using the T-BWSQ at the End of Study (EOS) visit. Subjects are asked about the presence/absence and severity of the symptoms listed in the questionnaire. For each listed symptom, the subject is to respond "No" (Score = 0), "Yes – moderate" (Score = 1) or "Yes – severe" (Score = 2).

The sum of responses will be the subject's total score. The total score will be summarized by treatment group using descriptive statistics. In addition, the number and percentage of subjects with a total score of ≥ 3 will be summarized using frequency count. Since this questionnaire is completed at the EOS visit only, this analysis will be performed at the EOS visit based on Safety Analysis set. The same analysis will be repeated for the subgroup based on the duration of exposure.

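### Rebound and withdrawal are measured from the calendar Follow-up Period, not from the last dose, so subjects who stopped drug early but stayed on study are analysed as newly withdrawn

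*SAP*

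**What the plan says.** **When Follow-up starts.** Protocol 9.1.2.3: "The Follow-up Period will begin at the end of Period 2". Protocol 9.1.2.2: "Period 2 will end with the completion of the 12-month visit". The anchor is a visit, not a dose.

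**Who is still in the study by then.** Under Protocol 9.5.5, subjects who stop study drug early are encouraged to continue all assessments except PK sampling, "including the Sleep Diary, and to return for all subsequent clinic visits, without the administration of study medication". The same section adds: "Subjects who discontinue early from study drug are considered on study as long as they return for their regularly scheduled visits".

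**Rebound.** SAP 3.4.2.4 takes sSOL and sWASO on each of the first 3 nights, the mean of those 3, and the first and second 7 nights of the Follow-up Period, all against Screening. The default efficacy population is the FAS (SAP 3.3). For the ANCOVA, SAP 3.4.2.4 says: "In this analysis, the treatment groups will be defined as the last randomized study treatment just before the Follow-up period". No rule refers to the last dose.

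**T-BWSQ.** The note on EOS, ET and EDD assessments in Protocol Table 3 reads: "except the T-BWSQ, which will not be conducted at EDD". SAP 3.6.7.2: "Since this questionnaire is completed at the EOS visit only, this analysis will be performed at the EOS visit based on Safety Analysis set". SAP Table 10 takes EOS as the nominal visit, with no limit on time since last dose. SAP 3.6.7.2 also repeats the analysis by duration of exposure.

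**The concern.** The stated objective is to evaluate rebound after treatment is discontinued, and Protocol 9.5.3 lists rebound among the safety-related assessments. Take a subject who stopped lemborexant at Month 4 and kept attending. On Follow-up nights 1 to 3 this subject is labelled with a lemborexant dose and analysed as just withdrawn, about 8 months after the last tablet. The nights that did follow the last dose are in the daily diary, but the rebound analysis does not use them. The same subject has no T-BWSQ at the EDD visit, and the EOS score is pooled with scores from subjects about two weeks off drug.

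At stake is what the rebound and withdrawal tables mean. As written they describe everyone who reached the Follow-up Period, and not the effect of stopping the drug.

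**Working it through.** **1. The plan's retention figures.** Protocol 9.7.2 and SAP 2 take 300 per arm, with discontinuation as high as 50% at Month 6 and 60% by Month 12.
- Month 6: 300 × (1 − 0.50) = 150 per arm.
- Month 12: 300 × (1 − 0.60) = 120 per arm.
- Six months on lemborexant: 2 × 150 + 120 = 420.

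All three agree with the documents, which give no figure for the rebound analysis itself.

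**2. Follow-up sample per lemborexant dose.** Grouping is by last randomized treatment, so placebo subjects re-randomized about 1:1 at Month 6 join the two lemborexant groups.
- On drug to Month 12: 120 + 120/2 = 180.
- Stopped lemborexant early: 180 + (150 − 120)/2 = 195.

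This assumes that placebo subjects who stopped in Period 1 are not re-randomized.

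**3. Share of the sample long off drug.** Let r be the fraction of the 195 who stay on study to Follow-up. The documents do not give r, so it is varied. The share is s = 195r / (180 + 195r). If stayers sit exactly at their Screening level, a true rebound of 10 minutes is observed as 10 × (1 − s).

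| r | stayers | s | 10 min reads as |
|---|---|---|---|
| 10% | 19.5 | 19.5/199.5 = 9.8% | 9.0 |
| 20% | 39 | 39/219 = 17.8% | 8.2 |
| 40% | 78 | 78/258 = 30.2% | 7.0 |

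**4. Milder case (assumed, not from the documents).** With 10% discontinuation by Month 6 and 15% by Month 12, both doses pooled:
- On drug to Month 12: 3 × 300 × 0.85 = 765.
- Stopped early: 2 × 300 × 0.15 + 300 × 0.05 = 105.
- r = 10%: 10.5/775.5 = 1.4%.
- r = 50%: 52.5/817.5 = 6.4%.

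A 10-minute rebound then reads as 9.9 to 9.4 minutes.

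**5. Effect on the strong-evidence rule.** SAP 3.4.2.4 asks that the lower 95% limit in Follow-up exceed the upper 95% limit at Screening. Use SD 33 minutes, the planning SD of change in sSOL, as a stand-in for the SD of the level. The observed rise needed is about 2 × 1.96 × 33/√n.
- Only the 180 newly withdrawn: 129.4/√180 = 9.6 minutes.
- With stayers, the true rebound needed is (129.4/√n)/(1 − s): 10.2, 10.6 and 11.5 minutes for r = 10%, 20% and 40%.

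**6. Direction.** Steps 3 to 5 rest on stayers being at Screening level. If they sleep worse than at Screening, they raise the Follow-up mean and the count of subjects past the 5-minute threshold, which adds apparent rebound. If newly withdrawn subjects still sleep better than at Screening, stayers at Screening level also raise the group mean.

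**The case against.** **The grouping sentence is a label, not a population rule.** Its evident job is to place re-randomized placebo subjects in an arm, and it is written for the ANCOVA. The protocol defines rebound as following completion of drug treatment and describes Follow-up as the time when subjects cease drug, which presumes they are still taking it. That is a fair reading of intent. But no rule turns the intent into a restriction, and the FAS default admits early stoppers.

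**A rule may exist elsewhere.** SAP 7 puts derivation rules in separate documents that are not available here, so a last-dose condition there cannot be excluded. Even so, a choice that defines a safety estimate belongs in the SAP. The SAP already uses the last dose elsewhere: for TEAEs (3.6.3) and for the Month 12 diary window of subjects who completed treatment (Table 9).

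**The number affected may be small.** The 50%/60% rates are a worst case used to check long-term exposure, not a forecast, and they do not separate stopping drug from leaving the study. Under Protocol 9.4.7.2, a subject who starts a new insomnia treatment must leave the study even if already off drug, which shrinks the pool. This stands, and it is why the milder range is shown.

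**The T-BWSQ is repeated by duration of exposure.** This separates a Month 4 stopper from a 12-month completer, but it is only a partial remedy because exposure length is not time since last dose. A 6-month stratum can mix placebo-to-lemborexant completers with lemborexant subjects who stopped at Month 6 and stayed.

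**A reader might infer that the plan biases these tables in the drug's favour.** The documents do not support that. It needs stayers to sit near Screening level, and nothing in either document says so.

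**Conclusion.** The gap is real. Neither document requires dosing up to the start of Follow-up, and neither counts rebound nights or T-BWSQ timing from the last dose. Followed as written, the plan mixes newly withdrawn subjects with subjects who may be months off drug. Only early stoppers who stay on study are at issue.

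The size is uncertain because the fraction who stay is not given. It could be negligible (1.4% of the sample) or material (30.2%) across the cases shown, and the direction is open. The dilution figures hold only if stayers are at Screening level.

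Rebound is a secondary endpoint outside the gate-keeping sequence, and withdrawal symptoms are an exploratory objective, so the primary and key secondary conclusions are untouched. The change should still be made, because these tables answer a safety question and the data needed are already collected.

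**What to change.** - In SAP 3.4.2.4 and 3.6.7.2, limit the main rebound and T-BWSQ tables to subjects who took study drug up to the start of the Follow-up Period, within a stated number of days.
- Count rebound nights (1, 2, 3, first 7, second 7) from the last dose, and apply the same population and grouping to the 5-minute proportions as to the ANCOVA.
- Show early stoppers separately and descriptively, using diary nights after their own last dose. State that these nights mix withdrawal with the reason for stopping, and that these subjects have no T-BWSQ near their last dose.
- Report how many subjects in the Follow-up sample fall in each category.

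The cost is SAP wording and programming. The last-dose date (Protocol 9.3.3) and the daily diary are already collected, so no new visits or data are needed. The downside is a somewhat smaller sample in the main tables.
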